Patient related outcomes (PRO) will be assessed using the following health related quality of life (HRQoL) assessments: • DLQI® • Patient's assessment of pain, itching and scaling • EQ-5D® • WPAI-PSO Safety assessments Safety will be assessed via the monitoring of physical examinations, vital signs, routine laboratory (clinical chemistry including urinalysis and hematology) data and adverse events (AEs). Other assessments The correlation between pharmacokinetic (PK) data and efficacy		
 EQ-5D[©] WPAI-PSO Safety assessments Safety will be assessed via the monitoring of physical examinations, vital signs, routine laboratory (clinical chemistry including urinalysis and hematology) data and adverse events (AEs). Other assessments The correlation between pharmacokinetic (PK) data and efficacy 		Patient related outcomes (PRO) will be assessed using the following health related quality of life (HRQoL) assessments:
WPAI-PSO Safety assessments Safety will be assessed via the monitoring of physical examinations, vital signs, routine laboratory (clinical chemistry including urinalysis and hematology) data and adverse events (AEs). Other assessments The correlation between pharmacokinetic (PK) data and efficacy		, , , , , , , , , , , , , , , , , , , ,
signs, routine laboratory (clinical chemistry including urinalysis and hematology) data and adverse events (AEs). Other assessments The correlation between pharmacokinetic (PK) data and efficacy		
· · · · · · · · · · · · · · · · · · ·	Safety assessments	signs, routine laboratory (clinical chemistry including urinalysis and
	Other assessments	

Data analysis

The Full Analysis Set for Treatment Period 2 of PASI 90 Responders (FAS-P90R) will include all patients who are rated as PASI 90 responders at Week 24, are randomized to treatment Group 1 or Group 2, and who received at least one dose of study drug at- or after Week 24.

The primary variable is the maintenance of the PASI 90 response rate at Week 52 in the FAS-P90R, ie the rate of patients who maintain their PASI 90 response assessed at Week 24 also at Week 52. The aim of the primary analysis for this study will be to demonstrate the non-inferiority of the 6-weekly dosing group compared to the 4-weekly dosing group, with respect to the primary endpoint in the FAS-P90R. The primary analysis will be performed comparing dosing groups (Group 1 vs Group 2) with respect to the primary efficacy variable in a logistic regression model with the factors treatment, country, body weight (< 90 kg or ≥ 90 kg), and PASI 90 response (Y/N) at Week 16. The odds ratio with its corresponding 95% confidence interval (CI) will be given (please notice that the upper limit of a 2-sided 95% CI is identical to the upper limit of a 1-sided 97.5% CI, which would correspond to a 1-sided test with a significance level of 2.5%). Additionally, a (1-sided) p-value for the shifted null-hypothesis will be computed.

The key secondary variable is the PASI 90 response rate at Week 52 in the FAS-P75P, ie, the proportion of patients with a PASI 75 response but also less than a PASI 90 response at Week 24 who achieve a PASI 90 response at Week 52. The key secondary analysis of this study will be to demonstrate superiority of the shortened 2-weekly dosing group compared to the 4-weekly dosing group in the FAS-P75P.

This analysis will be performed comparing dosing groups (Group 3 vs Group 4) with respect to the key secondary variable in a logistic regression model with the factors treatment, country and PASI response (75% to 82% or 83% to 89%) at Week 24. The odds ratio with its corresponding 95% CI and p-value will be presented. The key secondary analysis will be included in a confirmatory testing strategy.

For the safety evaluation, the patient groups of i/ PASI 90 responders and ii/ PASI 75 but not PASI 90 responders will be pooled; therefore, only 3 groups will be compared:

- secukinumab 300 mg s.c. every 2 weeks (patients from Group 4).
- secukinumab 300 mg s.c. every 4 weeks (patients from Group 1 pooled with Group 3).
- secukinumab 300 mg s.c. every 6 weeks (patients from Group 2).

Patients will be analyzed according to the treatment they received. Treatment emergent AEs will be summarized by system organ class (SOC) and preferred term.

Key words

Open-label, randomized, blinded assessment, chronic plaque psoriasis, PASI, secukinumab, monoclonal antibody

1 Introduction

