9.5 Analysis of secondary variables

9.5.1 Efficacy variables

The key secondary variable is the PASI 90 response rate at Week 52 in the FAS-P75P, ie, the proportion of patients with a PASI 75 response but also less than a PASI 90 response at Week 24 who achieve a PASI 90 response at Week 52. The key secondary analysis of this study will be to demonstrate superiority of the shortened 2-weekly dosing group compared to the 4-weekly dosing group in the FAS-P75P.

The statistical null-hypothesis to be rejected are that the odds ratio of gaining a PASI 90 response for patients on 2-weekly dosing versus patients on 4-weekly dosing = 1

Let π_i denote the probability of a PASI 90 response at Week 52 for treatment group j, j = 0, 1where

- 0 corresponds to 2-weekly dosing
- 1 corresponds to 4-weekly dosing

The following hypothesis will be tested

$$H_{0.2}$$
: $(\pi_0 / [1 - \pi_0]) / (\pi_1 / [1 - \pi_1]) = 1$ versus H_{A2} : $(\pi_0 / [1 - \pi_0]) / (\pi_1 / [1 - \pi_1]) \neq 1$

This analysis will be performed comparing dosing groups (Group 3 vs Group 4) with respect to the key secondary variable in a logistic regression model with the factors treatment, country and PASI response (75% to 82% or 83% to 89%) at Week 24. The odds ratio with its corresponding 95% CI and p-value will be presented.

The key secondary analysis will be included in a confirmatory testing strategy. The key secondary hypothesis will be a priori ordered below the primary hypothesis. This means that no multiplicity adjustment of the significance level is required; however, confirmatory evidence will be claimed only if non-inferiority with regard to the primary endpoint has been successfully demonstrated before. Otherwise, the result for the secondary endpoint will be interpreted as being purely explorative, independent of the nominal p-value.

The time course of PASI response (absolute points and percentage change from Baseline) will be graphically displayed for treatment Group 1 to 4 as well as for the total Treatment Period 1 set. All other secondary variables (IGA mod 2011, QoL) will be analyzed descriptively using means and SDs for continuous and absolute and relative frequencies for categorical variables.

Appropriate statistical tests for group comparisons of these variables will be defined in the SAP.

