9.7.1 Power for the key secondary objective

As per the sample size calculation for the primary objective, 1580 patients will be enrolled into Phase 1 of the study. In the secukinumab database (CAIN457A2302 and CAIN457A2303) 13.3% of patients were in the category of PASI 75 but did not achieve PASI 90 at Week 24. In the present study, this would translate into 210 patients fulfilling the criteria to be randomized into the partial responder part of the maintenance phase.

Prior Phase 3results (CAIN457A2302 and CAIN457A2303) suggest that the PASI responses reach a maximum at around 16 to 24 weeks with a sustained effect until Week 52. The PASI 90 responder rate at Week 52 of patients treated with secukinumab 300 mg s.c. every 4 weeks who have a PASI 75 but no PASI 90 response at Week 24 is estimated to be 3.8%. This rate may be increased by 14% (to then 18%) by increasing the dosing frequency to 2-weekly after Week 24.

A sample size of 210 patients (105 per group) will provide more than 90% power on a twosided, 95% significance level to detect differences in response rates for secukinumab intensified 2-weekly dosing compared to every 4 weeks, if the responder rates in these groups are about 4% vs. 18% at Week 52.

10 **Ethical considerations**

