#### 1.8.5 Key secondary analyses

Aim of the key secondary analysis, the PASI 90 response rate at Week 52 in the FAS-P75R, is the demonstration of superiority of the shortened 2-weekly dosing group compared to the 4-weekly dosing group in this patient set.

The statistical null-hypothesis to be rejected is that the odds ratio of gaining a PASI 90 response for patients on 2-weekly dosing versus patients on 4-weekly dosing = 1.

Let  $\pi_j$  denote the probability of a PASI 90 response at Week 52 for treatment group j, j=0, 1, where

- 0 corresponds to 2-weekly dosing
- 1 corresponds to 4-weekly dosing

The following hypothesis will be tested

$$H_{02}$$
:  $(\pi_0/(1-\pi_0))/(\pi_1/(1-\pi_1)) = 1$  versus  $H_{A2}$ :  $(\pi_0/(1-\pi_0))/(\pi_1/(1-\pi_1)) \neq 1$ 

This analysis will be performed comparing dosing groups (Group 3 vs. Group 4) with respect to the key secondary variable in a logistic regression model with the factors dosing group, country, body weight at Week 24 (< 90 kg or  $\ge 90 \text{ kg}$ ) and PASI response (< 83% vs.  $\ge 83\%$ ) at Week 24. The odds ratio with its corresponding 95%-Wald CI and the (two sided) p-value of the corresponding Wald statistic will be presented.

In case of subgroup analyses where the grouping variable is one of the above described factors in the logistic regression model the respective factor is excluded from the model.

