#### 2.2.2 Logistic regression

The analysis of the primary endpoint and of the key secondary endpoint will be performed using logistic regression models with factors dosing group, country and body weight at Week 24 (<90 kg or ≥90 kg). Potential further covariates in the model are specified in Section 1.8.2 and Section 1.8.5. Odds ratios will be computed for comparisons of secukinumab dosing regimens utilizing the logistic regression model fitted.

The odds ratios and their two-sided 95%-Wald confidence intervals will be computed utilizing the logistic regression model fitted. P-values will be given according to the descriptions in Section 1.8.2 and Section 1.8.5.

In case of subgroup analyses where the grouping variable is one of the above described factors in the logistic regression model the respective factor is excluded from the model.

The SAS procedure PROC LOGISTIC will be used for calculating logistic regression models. Dummy-coding will be performed with treatment reference category being 300 mg secukinumab every 4 weeks.

If the logistic regression model does not converge the following steps will be performed:

- 1. Run the PROC LOGISTIC procedure with EXACT statement;
- 2. If convergence not reached, remove the covariates from the model one by one until convergence is reached; start with removing country, followed by weight stratum and PASI 90 response at Week 16
- 3. If convergence not reached, perform Fisher's exact test.

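### The key secondary model splits the Week 24 PASI improvement at 83% although the measured value would cost the same one degree of freedom; the expected gain from using it is small

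*Protocol*

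**What the plan says.** Groups 3 and 4 take patients whose PASI has fallen from Baseline by at least 75% but less than 90% at Week 24 (protocol 3.1 and 5.2). The key secondary endpoint is a PASI 90 response at Week 52.

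The data analysis part of the protocol summary fits the key secondary logistic model "with the factors treatment, country and PASI response (75% to 82% or 83% to 89%) at Week 24", and protocol 9.5.1 says the same. SAP 1.8.5 keeps two levels, worded as "and PASI response (< 83% vs" 83% or more, and adds body weight at Week 24. SAP 1.1.1 records the added weight factor as a change from the protocol. Neither document explains the cut or gives the number of patients or responders expected on each side. Randomization is stratified by body weight only (protocol 5.3.1).

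On size, protocol 9.7.1 states: "A sample size of 210 patients (105 per group) will provide more than 90% power", "if the responder rates in these groups are about 4% vs. 18% at Week 52".

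If a logistic model does not converge, SAP 2.2.2 first runs exact logistic regression, then removes covariates one at a time, and finally uses Fisher's exact test. For the removal step the order is to "start with removing country, followed by weight stratum and PASI 90 response at Week 16". The section covers both the primary and the key secondary endpoint.

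**The concern.** The covariate and the endpoint lie on one scale. A patient at 89% at Week 24 needs one more percentage point to respond, and a patient at 76% needs 14. The planned model treats 83% and 89% as equal, and 82.9% and 83% as different. If the Week 24 value predicts Week 52 response, the split discards part of that information in a comparison with few responders.

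Nothing in the design calls for the split. The measured value exists for every randomized patient, because group assignment depends on it. The plan uses PASI as a measured quantity elsewhere: the ANCOVA of PASI has the baseline value as covariate (SAP 1.8.7), and the multiple imputation works from PASI changes (SAP 2.2.3).

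A little power is at stake in the one secondary hypothesis that belongs to the confirmatory testing sequence (SAP 1.8.6).

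**Working it through.** **Inputs from the documents.** 105 patients per group, response rates 4% (4-weekly) and 18% (2-weekly), from protocol 9.7.1; two-sided 5% level, from SAP 1.8.6. Expected responders: 105 × 0.04 = 4.2 and 105 × 0.18 = 18.9, about 23 in total.

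**The plan's own figure.** Two-proportion test with pooled variance under the null, mean rate 0.11:

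z = [0.14 × √105 − 1.96 × √(2 × 0.11 × 0.89)] / √(0.04 × 0.96 + 0.18 × 0.82) = (1.4346 − 0.8673) / 0.4313 = 1.315, so power is 90.6%.

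The stated figure of more than 90% reproduces.

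**Effect of the coding.** The distribution of the Week 24 value and its link to response are not in the documents, so they were varied. Each scenario has 2000 simulated trials at the planned rates. Logistic models with treatment plus either the 83% band or the measured value were fitted to the same trials (country and weight left out), and the Wald test was applied.

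| Assumed distribution (share below 83%) | Odds ratio, 75% to 90% | Power, band | Power, measured | Gain (points) |
|---|---|---|---|---|
| Uniform (53%) | 1 | 90.8 | 91.0 | 0.2 |
| | 4.5 | 89.9 | 90.4 | 0.5 |
| | 20 | 91.5 | 91.7 | 0.2 |
| | 90 | 92.4 | 93.6 | 1.2 |
| Skewed towards 90% (31%) | 1 | 91.0 | 91.0 | 0.0 |
| | 4.5 | 89.8 | 90.2 | 0.4 |
| | 20 | 90.0 | 90.3 | 0.3 |
| | 90 | 90.2 | 91.6 | 1.4 |
| Skewed towards 75% (75%) | 1 | 90.3 | 90.1 | −0.2 |
| | 4.5 | 91.7 | 91.8 | 0.1 |
| | 20 | 91.6 | 92.2 | 0.6 |
| | 90 | 94.0 | 93.8 | −0.2 |

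Simulation error is about 0.6 points per power estimate.

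Two further simulations agree:
- 8000 trials per scenario, odds ratio 2 to 5 per 5 points, uniform or skewed towards 90%: gain 0.3 to 1.0 points. Trials with no Group 3 responder were skipped (0.96^105 = 1.4% of trials), which raises the power level slightly under both codings.
- A paired simulation with weight and five assumed countries in the model, same odds ratios: gain −0.1 to +1.3 points. Where the two codings led to different test decisions, the measured value was favoured 214 to 125. The gain is roughly nil if the Week 24 value is not prognostic.

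**Where the gain comes from.** In the uniform scenario with odds ratio 90, the median treatment log odds ratio is 1.82 (median standard error 0.586) with the band and 1.91 (0.602) with the measured value. The ratios are 1.82/0.586 = 3.11 and 1.91/0.602 = 3.17. The test gains because the conditional estimate grows by more than its standard error. The confidence interval on the log scale does not become narrower.

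**What an empty lower band would do.** Suppose 0 of 105 patients respond below 83%, and above it 4 of 52 respond in Group 3 and 19 of 53 in Group 4. In the fitted model the band coefficient runs off. The treatment log odds ratio stays at ln[(19/34)/(4/48)] = 1.90, with standard error √(1/19 + 1/34 + 1/4 + 1/48) = 0.59, the same as in the upper band alone.

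**How likely that is.** Let s be the share of patients below 83%, and p3 and p4 the response rates there in Groups 3 and 4. The chance of no responder is (1 − s·p3)^105 × (1 − s·p4)^105. With s = 0.5 and a between-band odds ratio of 3, p3 = 0.0206 and p4 = 0.1033, so 0.9897^105 × 0.9484^105 ≈ 0.1%. For odds ratios 5 and 10 it is 0.9% and 6%. With one third of patients below 83%, odds ratios 3, 5 and 10 give 2.4%, 8.5% and 26%. If both arms respond at 4% and s = 0.5, they give 11%, 23% and 44%.

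**Removal order against model.** The key secondary model contains dosing group, country, weight and Week 24 PASI response. The removal list contains country, weight and Week 16 PASI 90 response. The last is a primary-model factor, and the Week 24 factor is not named.

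**The case against.** The best defence is that a prespecified two-level covariate is legitimate and common, and matches the plan's other binary factors (weight at 90 kg, Week 16 PASI 90 response). The gain is close to simulation noise and rests on assumed inputs. A linear term brings its own assumption. Protocol 3.2 itself notes measurement variability in PASI, so a one-point difference between patients should not be over-read. All of this stands. It limits the size of the benefit but gives no reason to prefer the split.

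A reader might infer more than the documents support:
- *That a lower band without responders would break the analysis.* Only the band coefficient diverges; the treatment odds ratio and its Wald test survive.
- *That country and weight would then be dropped first to no purpose.* Exact logistic regression comes before any covariate is removed. Country is in any case a likelier source of empty levels: assuming equal-sized countries at the planned rates, the chance of at least one without responders is about 3% with 5 countries, 30% with 8 and 57% with 10. Recoding PASI would not change that.
- *That values between 82% and 83%, or between 89% and 90%, belong to no band.* This is true of the protocol wording, but SAP 1.8.5 classifies every value.
- *That the Week 24 value is the strongest baseline predictor.* It is plausible, but neither document gives any association with Week 52 response in this group.

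**Conclusion.** The point holds as a minor improvement to the analysis. The model splits a measured covariate that is on the endpoint's own scale, without a stated reason and without saving a degree of freedom. The expected benefit is about 0 to 1.4 percentage points of power. It lies at the upper end only when the Week 24 value predicts very strongly, and is about nil when it does not predict. These figures depend on assumed distributions and slopes.

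The stated sample size and power are unaffected, and nothing here suggests bias in the treatment odds ratio. Separation is not part of the case for change. The mismatch in the SAP 2.2.2 removal order is a wording error. It matters only if exact regression has also failed.

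**What to change.** In SAP 1.8.5, replace the two-level factor by the Week 24 percentage improvement in PASI from Baseline as a continuous linear covariate, and keep the 83% split for descriptive tables. List the change in SAP 1.1.1 beside the added weight factor, and settle it before outcomes are looked at by group. If the sponsor keeps the split as primary, a prespecified sensitivity analysis with the measured value is a reasonable alternative.

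In SAP 2.2.2, give the key secondary model its own removal order: name the Week 24 PASI covariate and confine the Week 16 PASI 90 factor to the primary model.

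The cost is SAP wording only, with no new data and no extra parameter. The downside is the assumption of linearity on the logit scale over 75% to 90%. The reported odds ratio would also be conditional on the measured value instead of the band, so it may differ slightly in size.

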1.1 Background

Psoriasis is a chronic, immune-mediated inflammatory disease that affects up to 3% of the population worldwide (Jacobson et al 2011). Psoriasis typically manifests as plaques (Lebwohl 2003) that occur most commonly on the skin of the elbows and knees. Plaques can affect any area, including the palms and soles (Pettey et al 2003); fingernails and toenails are also commonly affected (Radtke et al 2011). The efficacy of systemic therapy with biologics in the treatment of moderate-to-severe plaque psoriasis is well established (Christophers et al 2013; Herrier 2011).

Secukinumab is a fully human immunoglobulin G1/κ-class (IgG) anti-interleukin (IL)-17A monoclonal antibody that selectively suppresses the inflammatory cascade induced by the cytokine IL-17A. Secukinumab has demonstrated efficacy and safety for the treatment of moderate-to-severe plaque psoriasis (Langley et al 2014; Paul et al 2014). A large proportion of patients (71%) with moderate to severe plaque psoriasis achieved a Psoriasis Area and Severity Index (PASI) 90 response after 16 weeks of treatment with secukinumab 300 mg s.c. Subcutaneous injections were administered every 4 weeks with the exception of the first 4 weeks of treatment when the drug was given weekly. A sustainable drug response was still evidenced at Week 52 with a PASI 90 response rate of 63%. The Investigator Global Assessment modified 2011 (IGA mod 2011; Langley et al 2013) 0/1 response rate was comparable to the PASI 90 response with approximately 74% and 64% of patients achieving a clinical response at Week 16 and Week 52, respectively (pooled data from CAIN4572302 and CAIN4572303 pivotal studies). The Phase 3 clinical trials data support the use of secukinumab 300 mg s.c. every 4 weeks for maintenance of clinical response.

Optimizing maintenance dosing regimens for patients treated with (biologic) drugs offers many benefits, such as minimizing patients' exposure to the drug substance, increasing drug compliance and lessening economic burdens while keeping an acceptable clinical response. This principle has been investigated in a number of studies mainly in rheumatic disorders with currently available biological drugs. One psoriatic arthritis study demonstrated that most patients maintained their initial clinical response when the maintenance dose interval was prolonged from 2 weeks to 4 weeks after an initial induction period (Cantini et al 2012). Similar dose reductions have been reported in rheumatoid arthritis (den Broeder et al 2002) and in ankylosing spondylitis patients (Lee SH et al 2008). In these studies the original dosing interval was maintained but the dose was reduced. Dermatologists, like rheumatologists, are looking for a similar reduction and optimization in drug exposure once a patient has cleared, or almost cleared, skin from psoriasis. However, only one double-blind study investigating dose reduction of a biologic drug in psoriasis was identified in the literature which showed that the initial clinical response was maintained despite reducing the dose by 50% after 12 weeks (Papp et al 2005).

In contrast, patients not responding adequately to a biologic treatment can benefit from an increased frequency of drug dosing. Shortening dose intervals (off-label use) for marketed substances can be assumed to happen frequently especially in partial responders in daily practice. One study described that reducing the dosing interval (of ustekinumab) from 12 weeks to 8 weeks in partial responders had a good clinical effect (Kimball et al 2012).

biological treatment (Papoutsaki et al 2007).

Similarly, another study demonstrated that shortening the dose interval (of adalimumab) from 2 weeks to 1 week was effective in patients who were refractory to both non-biological and

At the present time clinical studies assessing flexible dosing regimens for long-term secukinumab treatment are very rare. A retreatment-as-needed (RAN) approach (ie, retreatment at start of relapse) has been assessed as an alternative to maintain response in some patients while adjusting drug exposure. The SCULPTURE (CAIN457A2304) study compared secukinumab RAN to a fixed-interval regimen (every 4 weeks) for the maintenance of efficacy up to 52 weeks in patients who achieved a PASI 75 response at Week 12 with secukinumab. The SCULPTURE study did not confirm the RAN dosing regimen as non-inferior to a fixed interval dosing regimen of secukinumab in plaque-type psoriasis even though both regimens led to clinically meaningful response rates. The fixed-dose interval regimen was shown to have clear benefits compared to the RAN regimen for sustained efficacy in the treatment of psoriasis (Mrowietz et al 2013). Consistently across efficacy measures, patients in the fixed-interval groups showed increased maintenance of response over those in the RAN groups. These results indicate that fixed-dose interval regimens are preferable over RAN regimens for maintenance dose regimens of secukinumab. Varying the duration of the fixed-dose interval of secukinumab in the maintenance period could potentially allow a better alternate approach for flexible dosing than the RAN approach and this will be investigated in the current study.

